### 14.2. Case-control study

The case-control study seeks to estimate the difference in biomarker values between mTBI patients and healthy controls. We aim to recruit 100 healthy controls and 100 mTBI patients for this nested study. For example, with this sample size we would have more than 90% power to detect a difference for a biomarker with a mean value of 2 for the controls and a mean value of 3.5 for the mTBI patients (mean difference is 1.5), assuming a standard deviation of 3 units. Alternatively, with a binary outcome, such as headache presence, we would again have more than 90% power with the planned number of individuals if the percentage with headache in the healthy participants was 3% and the odds ratio comparing mTBI and healthy was 4.

We will estimate the difference between the healthy and mTBI patients for each of the biomarkers using linear regression for the continuous biomarkers, with transformation of the biomarker values if appropriate, and logistic regression for the binary outcomes. The regression models used for these analyses will be adjusted for any known clinical confounders as appropriate.

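### Section 14.2 claims more than 90% power for a binary biomarker at 3% in controls and an odds ratio of 4, but 100 per group gives about 60%

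*Protocol*

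**What the plan says.** Protocol section 14.2 (Case-control study) sets the size: "We aim to recruit 100 healthy controls and 100 mTBI patients for this nested study". It then gives two illustrations of what that size offers.

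- **Continuous biomarker:** means of 2 and 3.5 ("mean difference is 1.5), assuming a standard deviation of 3 units"), with power above 90%.
- **Binary outcome, such as headache presence:** "more than 90% power with the planned number of individuals if the percentage with headache in the healthy participants was 3" per cent, on the further condition that "the odds ratio comparing mTBI and healthy was 4".

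The planned analysis is linear regression for continuous markers and "logistic regression for the binary outcomes". Section 14.2 gives no significance level, sidedness or dropout allowance for either illustration.

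**The concern.** All the inputs to the binary claim except alpha are printed in one paragraph, so it can be checked directly. With 3% in controls, 100 controls yield about 3 events, and an odds ratio of 4 yields about 11 events among 100 patients. A comparison of 3 with 11 events is unlikely to have 90% power.

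This is the only power statement for binary markers in nested study 2. Several such markers are on the list: PTSD yes/no from the PCL-5 is the primary mental health biomarker in Table 2, and Appendix 1 adds headache presence and PTSD yes/no from the MINI. Low control prevalence is plausible for PTSD, because section 4.2.2 excludes controls with a prior diagnosis. Section 14.3 provides case-control information to the Delphi panel that reduces the candidate list. Anyone relying on the printed figure would put the chance of missing such an effect below 10%, when at the stated inputs it is about 40%. A useful binary marker could then be set aside too readily.

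**Working it through.** **Inputs from section 14.2:** n = 100 per group; control proportion p1 = 0.03; odds ratio 4; claimed power above 90%.

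**Assumptions, because the section is silent:** two-sided alpha 0.05 (varied in step 4) and no dropout, which is the most favourable case for the claim.

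**1. Check the convention on the continuous example.** Standardised difference d = 1.5/3 = 0.5. Power ≈ Φ(d√(n/2) − 1.96) = Φ(0.5 × 7.071 − 1.96) = Φ(1.576) = 94.2% (94.0% with the t distribution). This agrees with the protocol's statement, so two-sided 5% fits that example.

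**2. Proportion implied in the mTBI group.** p2 = 4 × 0.03 / (0.97 + 4 × 0.03) = 0.12/1.09 = 0.1101, so the difference is 0.0801.

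**3. Power for 3% v 11.0%, 100 per group, two-sided 5%.**

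Pooled normal approximation:
- Mean proportion = (0.03 + 0.1101)/2 = 0.0700.
- SE under the null = √(2 × 0.0700 × 0.9300/100) = 0.0361.
- SE under the alternative = √(0.03 × 0.97/100 + 0.1101 × 0.8899/100) = 0.0356.
- Power = Φ((0.0801 − 1.96 × 0.0361)/0.0356) = Φ(0.262) = 60.3%.

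Wald test on the log odds ratio, the closest to unadjusted logistic regression:
- SE = √(1/3 + 1/97 + 1/11.01 + 1/88.99) = 0.668.
- Power = Φ(ln 4/0.668 − 1.96) = Φ(2.076 − 1.96) = 54.6%.

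| Test, two-sided 5% | Power |
|---|---|
| Yates-corrected chi-square, exact enumeration | 49.2% |
| Fisher, exact enumeration | 52.1% |
| Wald, log odds ratio | 54.6% |
| Pooled z | 60.3% |
| Unpooled z | 61.3% |
| Pearson chi-square, exact enumeration | 62.6% |
| Arcsine | 64.1% |
| Likelihood ratio, exact enumeration | 65.1% |

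**4. Could another reading give 90%?** Using the pooled z formula:

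| Reading | Power |
|---|---|
| One-sided 5% | 71.9% |
| One-sided 10% | 82.9% |
| The 4 taken as a risk ratio (3% v 12%) | 67.8% |
| 200 per group instead of 200 in total | 88.4% |
| All 610 main-study patients v 100 controls | 78.8% |

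None reaches 90%.

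**5. What would give 90% (two-sided 5%)?**
- At 3% and odds ratio 4: 212 per group (236 with continuity correction); 80% power needs 159.
- At 100 per group and 3% in controls: odds ratio about 6.4 by pooled z, or about 5.9 by exact Pearson.
- At 100 per group and odds ratio 4: about 7.1% in controls (implying about 23.4% in patients).

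**The case against.** The arithmetic has no defence, and nothing elsewhere in the protocol corrects it. The case on the other side is about weight.

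- **It is only an illustration.** The study is framed as estimating differences, both power statements are offered as examples, and the 100 + 100 is not said to derive from the binary one. This stands: the design does not collapse and the continuous example holds.
- **Headache itself is probably well powered.** The background cites rates above the 11% implied here: 22% at 3 months in Table 1, and 30% to 90% prevalence in section 1.3.1. Keeping 3% in controls, 100 per group gives 85% power at 15% in patients, 92% at 17%, 98.6% at 22% and over 99.9% at 30%. This stands as context for headache, although those are background rates under varying definitions. It does not make the printed claim true, and headache is named only as one instance of a binary outcome.
- **The Delphi has no significance rule.** Section 14.3 asks for judgements on prognostic capability, with case-control information supplied as needed. This also stands: wrongly discarding a marker is a possibility and is not built into the plan.
- **Alpha is not given.** Two-sided 5% is an assumption, but step 4 of the working shows that the conclusion does not depend on it.

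**Conclusion.** The concern holds. At the stated inputs the power is about 60%, not above 90%, which is a shortfall of about 30 percentage points. Across standard two-sided 5% tests it lies between 49% and 65%. Taking the pooled z, exact Pearson, Fisher and Wald results (52% to 63%), the chance of missing the stated effect is 37% to 48%, against the under 10% implied. The result assumes a two-sided 5% level, equal groups of 100 and no dropout; any dropout would lower it further. The error is confined to the binary illustration. It does not affect the continuous example, the main study's sample size or any analysis method.

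**What to change.** Replace the binary sentence in section 14.2 with one of the following, and state the alpha and sidedness for both examples:

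- with 100 per group, 3% in controls and an odds ratio of 4, power is about 60%; or
- with 100 per group, 90% power is available for an odds ratio of about 6 at 3% in controls (5.9 to 6.4 depending on the test), or for an odds ratio of 4 when about 7% or more of controls are positive, up to moderate prevalences.

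It would also be sensible to give the corrected figure to the Delphi panel alongside the case-control results, so that a non-significant binary marker is not read as evidence of no difference.

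The cost is one sentence and a less favourable stated figure. No extra enrolment, procedure or analysis is needed.

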## 14.3. Reduction of candidate biomarkers

To move to the next stage of evaluation, where a prognostic model will be produced, it will be necessary to reduce the number of candidate biomarkers. To do this we aim to use a modified Delphi approach, where we will survey all clinical study co-applicants in addition to clinical experts independent of the study. In the first round of the Delphi process we will ask for judgements on the prognostic capability of the investigated biomarkers, and we will progress through rounds until we reach consensus. Delphi participants will be provided with information from the variability and case-control studies to inform their decisions as necessary.

### 14.4. Development of a prognostic model

We aim to develop multivariable statistical models that can predict sequelae of mTBI using the investigated biomarkers. The sequelae of mTBI being examined are headache, vestibular dysfunction, mental health (depression, PTSD), cognition, global function and full return to work, play or duty. These clinical outcomes are measured via mean monthly headache days, vestibular disturbance questionnaire, self-reported PHQ-9, self-reported PCL-5, corrected global composite score, and MPAI, respectively. Global composite score and MPAI are continuous outcomes; monthly headache days is a count outcome; and clinical thresholds to PHQ-9 and PCL5 will categorise patients into those with and without depression and PTSD respectively (binary outcomes). Each of these outcomes will be measured at 6-, 12- and 24-months post-injury.

Whilst absolute values of biomarkers will be valuable all biomarkers are measured on multiple occasions, as such characteristics such as the rate of change of biomarkers and time until normalisation will also be considered as potentially important data in their own right.

We aim to recruit 610 participants to follow-up for the prognostic modelling phase of the project. At 6 months, for each of the headache, depression and PTSD outcomes, we will have sufficient sample size to investigate a model with 10 candidate parameters; for the global composite score and MPAI outcomes, we will have sufficient sample size to investigate a model with 44 parameters. Sample size calculations were based on methods proposed by Riley [222, 223]. This will allow for 10% drop out which will be reviewed, and the analysis plan modified accordingly.

Depending on the type of outcome, various types of statistical modelling approaches will be used. For example, continuous, binary and count outcomes will be modelled using linear, logistic and Poisson regressions respectively. We will build multivariable models that can predict clinical outcomes primarily at 6 months (secondarily, we may investigate outcomes at 12 and 24 months), based on 21-day biomarker data. We will also examine how changes to these biomarkers from 21 days to three months affect the clinical outcome. Models will be developed in line with best practice, using multiple imputation, backwards selection, and multivariable fractional polynomials in the development, as appropriate. We will internally validate the models produced using bootstrapping techniques and allow for optimism by applying a uniform shrinkage factor. Any multivariable models produced will be checked for compliance to model assumptions. Model performance will be assessed in terms of prediction and calibration, for example C-index for the logistic models.

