## 1.4. Workstream 2, mental health

### 1.4.1. Background

People who have suffered TBI experience higher rates of co-morbid mental health outcomes. In mTBI, 1 in 5 experience mental health disorders at 6 months post injury [62], with a 3-fold increase in the risk of developing a mental illness in the first 6 months post-mTBI [63]. Further, military personnel who experience mTBI are at a significantly increased risk of PTSD, depression and anxiety 3 to 6 months after deployment [64]. PTSD and depression are the most frequent, occurring in up to 50% and 60% of patients respectively [65]. PTSD, as per the Diagnostic and Statistical Manual of Mental Disorders, Fifth Edition (DSM-5) criteria is characterised as exposure to a traumatic event with the presence of intrusion symptoms, avoiding stimuli associated with the event, negative alterations in cognition and mood, and hyper-arousal [66]. We have previously demonstrated several clinical variables that are associated with increased risk of PTSD post-mTBI, including mode of injury (e.g. assault), severity of injury, and pre-existing mental health disorder [67]. Rates of completed suicide are also significant, with the relative risk of suicide post-TBI almost 3 times higher than the general population [68]. Poor mental health contributes uniquely to the burden of living with TBI, with some indication that mental health problems precede functional decline. Hence, better understanding of the aetiology of PTSD and depression post-mTBI could lead to targeted

preventative treatments with significant and wide impact.

Whilst we have previously shown that self-reported outcomes of TBI are more sensitive to patient needs than objective outcome scores [69], the subjective nature of conventional diagnostic methods for PTSD and the high comorbidity of depression mean that an objectively measurable biomarker for diagnosing PTSD would be particularly impactful to clinicians and researchers.

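### Section 14.4 models PHQ-9 and PCL-5 only after cutting them to yes/no, which loses about 36–51% of the outcome information if 20–60% of patients are above threshold; a full-score model should sit beside the logistic one

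*Protocol*

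**What the plan says.** Section 14.4 sorts the 6-, 12- and 24-month outcomes by type. The cognitive composite and MPAI stay continuous and monthly headache days is a count. For the two mental health scales, "clinical thresholds to PHQ-9 and PCL5 will categorise patients into those with and without depression and PTSD respectively (binary outcomes". The next paragraphs give as an example that "continuous, binary and count outcomes will be modelled using linear, logistic and Poisson regressions respectively".

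On size, "We aim to recruit 610 participants to follow-up for the prognostic modelling phase of the project", and "This will allow for 10% drop out which will be reviewed". The protocol then says that "for each of the headache, depression and PTSD outcomes, we will have sufficient sample size to investigate a model with 10 candidate parameters", and that "for the global composite score and MPAI outcomes, we will have sufficient sample size to investigate a model with 44 parameters". It cites published minimum-sample-size methods for prediction models. It does not give the R², shrinkage target or outcome proportions that were used.

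PHQ-9 and PCL-5 are completed in the remote battery (section 7.6.1), which is repeated at 6, 12 and 24 months (sections 7.9 to 7.11). Full scores will therefore exist. Section 9.1 lists depression and PTSD among the secondary outcomes. For prevalence, section 1.4.1 says: "In mTBI, 1 in 5 experience mental health disorders at 6 months post injury". The same section puts PTSD at up to 50% and depression at up to 60%.

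**The concern.** Once a score is cut, a patient just above the threshold counts the same as one far above it, and a patient just below counts the same as one with no symptoms. The variation inside each group, which a biomarker could help to explain, no longer enters the model. The protocol gives no reason for using only the cut version.

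A yes/no answer does not require a yes/no model. An ordinal model of the score yields the predicted probability of being at or above any threshold, which is the quantity a clinician would use.

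At stake are the chance of recognising a truly prognostic biomarker for two named secondary outcomes, and the precision of the fitted prediction models. The point concerns these scales as outcomes, not how PCL-5 is coded as a predictor.

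**Working it through.** **Inputs from section 14.4.** 610 recruited and 10% dropout, so 610 × 0.9 = 549 analysed; 10 parameters for headache, depression and PTSD; 44 for the two continuous outcomes.

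**Assumptions.** Shrinkage target S = 0.9; a roughly normal underlying score; two-sided 5% tests; the proportion above threshold q varied from 10% to 60%. The 20% point is the 1-in-5 figure in section 1.4.1, which is for any mental health disorder rather than for either scale. The 50% and 60% points are that section's upper figures.

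**1. The plan's own figures.** The shrinkage criterion is p = n(S − 1) ln(1 − R²/S). With Cox-Snell R² = 0.15, p = 549 × 0.1 × [−ln(1 − 0.15/0.9)] = 54.9 × 0.1823 = 10.0. The continuous-outcome criterion gives 44 at R² = 0.50. Both R² values were found by solving backwards. The match shows that they are compatible with the plan, not that the plan used them.

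**2. Information kept by the cut.** E = φ(z)² / [q(1 − q)], where z is the normal quantile at the cut. At q = 0.20, φ(0.842) = 0.280, so E = 0.0784/0.16 = 0.49.

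**3. Power after the cut.** A biomarker with 80% power on the full score has an expected z-value of 1.96 + 0.84 = 2.80. After the cut this becomes 2.80√E, and power is Φ(2.80√E − 1.96). At q = 0.20, 2.80 × 0.70 = 1.96, so power is 50%.

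**4. Model size for the same signal.** A latent-normal link converts Cox-Snell R² = 0.15 on the cut outcome to the R² of the uncut score. Two criteria then give the number of parameters that 549 patients support: the formula in step 1, and the full continuous-outcome criterion.

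| Above threshold | Information kept | Lost | Power (80% on full score) | Equivalent score R² | Parameters, step 1 formula | Parameters, continuous criterion |
|---|---|---|---|---|---|---|
| 10% | 0.342 | 66% | 37% | 0.425 | 35 | 36 |
| 20% | 0.490 | 51% | 50% | 0.303 | 22.5 | 24 |
| 30% | 0.576 | 42% | 57% | 0.259 | 18.6 | 20 |
| 50% | 0.637 | 36% | 61% | 0.235 | 16.6 | 18 |
| 60% | 0.622 | 38% | 60% | 0.241 | 17.1 | 19 |

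The last three columns are illustrative. They apply to a continuous score and are not a sample-size calculation for an ordinal model.

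**5. Does it survive skew?** A simulation used 549 patients, an exponential-shaped 0–27 score and a biomarker correlation of 0.12 (3,000 runs). Power was about 77% on ranks (as an ordinal model would use) against 55% on the cut with about 23% above it, and 75% against 36% with about 10% above it. The shape and the correlation are assumptions.

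**6. Does it improve prediction of the threshold itself?** A simulation used 549 patients, 10 predictors, 20% above the cut and proportional odds true. Before any shrinkage correction, the ordinal model moved the mean validation calibration slope from 0.81 to 0.91 (ideal 1) and the C-index from 0.680 to 0.689. The gain is mostly in calibration, with little in discrimination.

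**The case against.** The strongest defence is that yes/no is the intended target. Section 9.1 names depression and PTSD, Table 2 lists PCL-5 as PTSD yes/no, and section 14.4 judges models on prediction and calibration, not on power to detect a biomarker. MPAI and the cognitive composite have no case definition here, so treating them differently is not an inconsistency. This stands. It justifies keeping the logistic model, but it does not rule out a full-score model that reports the same probability.

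Proportional odds can also fail. A biomarker might act differently on mild symptoms than at the threshold, and the predicted probability there would then be miscalibrated. Logistic regression targets that probability directly. This stands too, and is why the logistic model should remain as comparison and fallback.

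Three stronger readings are tempting, and the protocol does not support them:

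- *The cut halves the model size that 610 patients can support, or causes the limit of 10.* Headache is described as a count, is not cut, and also gets 10. The R², shrinkage target and proportions behind 10 are not stated.
- *The gap between 10 and 44 is the price of the cut.* Under the back-solved values it mostly reflects a different assumed R² (0.15 against 0.50).
- *Ten parameters must cope with the whole Appendix 1 list.* Section 14.3 reduces the candidates by a Delphi process before any model is built.

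A separate analysis plan may already include a full-score analysis. The point concerns only what the protocol states.

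**Conclusion.** The point holds as an inexpensive gain in efficiency, not as an error: a logistic model of a clinical threshold is valid. The size of the loss rests on a roughly normal underlying score and on an unstated proportion above threshold. An unconditional claim that half the information is lost would go too far, because that figure belongs to 20% prevalence and the 1-in-5 source is not specific to either scale. The loss is nevertheless at least 36% at every proportion examined.

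On model size, only a conditional statement is possible. If 10 parameters reflects Cox-Snell R² of 0.15, S of 0.9 and 549 analysed, the same signal on a continuous score would support roughly 17–24 parameters at 20–60% prevalence. The outcomes are secondary, which limits the weight of the point.

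**What to change.** In section 14.4:

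- Add a proportional-odds (ordinal) model of the full PHQ-9 and PCL-5 scores at 6 months, and at 12 and 24 months if those are analysed.
- From that model, report the predicted probability of being at or above the clinical threshold, with its C-index and calibration.
- Keep the logistic model of the binary outcome alongside, as the comparison and as the fallback if proportional odds fails near the threshold.
- State the outcome proportion, R² and shrinkage target behind the candidate-parameter limit. Raise the limit only for the full-score model, and only after a calculation made for that model.

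The cost is wording in section 14.4 and the analysis plan, a little more analysis and a proportional-odds check. No new data, visits or participants are needed.

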## 7.8. 3-month assessment – Visits 7-10

If this is their enrolment point into the study, participants will:

- Receive the study actigraphy device and training in how to use it
- Receive training in how to install and use the study app

The study assessments at 3 months will be split into individual days for remote assessments (visit 7 – outlined in 7.6.1), clinical assessments (visit 8 – outlined in 7.6.2, minus hair collection), imaging assessments (visit 9 – outlined in 7.6.3), and exploratory imaging (visit 10 – outlined in 7.6.4).

*Note:* Only those mTBI patients entering the study at 3 months will complete demographic details and physical health components of the clinical assessment visit (as detailed in 7.6.2).

Visit 10 will be discontinued after 50 mTBI patients and 50 healthy controls have completed the visit.

## 7.9. 6-month assessment – Visit 11 & 12

The study assessments at 6 months will be split into individual days for remote assessments (visit 11 – outlined in 7.6.1) and clinical assessments (visit 12 – outlined in 7.6.2) in addition to a short remote interview with a study researcher (*Note: the MINI for DSM-5 will only be performed if the participant registers a score of*  $\geq$  50 *in the* PCL-5). One month prior to the visit day, mTBI patients will be

reminded to wear their actigraph for 2 weeks and asked to complete daily headache and sleep diaries for 28 days, as detailed in 7.6.1. Over this period, participants will also complete weekly mini-cognition battery assessments. The study app will send reminders to complete these assessments.

*Note:* Participants will not complete the medical history components of the clinical assessment visit (as detailed in 7.6.2).

Visit 12 will be discontinued after 100 mTBI patients have completed it.

## 7.10. 12-month assessment – Visits 13

The study assessment at 12 months (visit 13) will consist of remote assessments as per section 7.6.1 in addition to a short remote interview with a study researcher. One month prior to the visit day, participants will be asked to complete daily headache and sleep diaries for 28 days, as detailed in 7.6.1. Over this period, participants will also complete weekly mini-cognition battery assessments. The study app will send reminders to complete these assessments.

## 7.11. 24-month assessment – Visit 14

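### Plain Poisson regression with backwards selection fits a 0–28 headache-day count badly and would probably keep noise biomarkers far above the nominal rate

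*Protocol*

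**What the plan says.** Protocol section 14.4 sorts the clinical outcomes by type. Two are continuous, depression and PTSD are made binary by thresholds, and "monthly headache days is a count outcome". No other outcome is called a count. The modelling paragraph then says, as an example, that "continuous, binary and count outcomes will be modelled using linear, logistic and Poisson regressions respectively". Models are to be developed "using multiple imputation, backwards selection, and multivariable fractional polynomials in the development, as appropriate". No retention p-value is given, and no overdispersed, zero-inflated or bounded-count model is named.

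The same paragraph contains safeguards: "Any multivariable models produced will be checked for compliance to model assumptions". There is also bootstrap internal validation, and the plan will "allow for optimism by applying a uniform shrinkage factor".

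The headache count comes from the app diary. For the 6-month assessment (section 7.9) participants are "asked to complete daily headache and sleep diaries for 28 days". Sections 7.10 and 7.11 repeat this for 12 and 24 months.

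On size: "We aim to recruit 610 participants to follow-up for the prognostic modelling phase of the project", and "This will allow for 10% drop out". The headache model is allowed 10 candidate parameters.

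**The concern.** Poisson regression takes the variance to equal the mean and sets no upper limit on the count. Headache days from a 28-day diary cannot exceed 28. Many patients are likely to record none while others record many. The variance is then several times the mean, model-based standard errors are too small, and the tests that drive backwards selection are too liberal.

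Persistent post-traumatic headache is a named secondary outcome (section 9.1), and the programme exists to find out which biomarkers carry prognostic information. A selection step that keeps uninformative biomarkers at several times the nominal rate works directly against that aim for the headache model. The primary outcome, return to normal activity, is not a count and is not affected.

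**Working it through.** **Step 1. The plan's own numbers.** 610 × 0.90 = 549 patients analysed. The figure of 10 parameters is reproduced by the shrinkage criterion n = p / ((S − 1) ln(1 − R²/S)). With p = 10, S = 0.9 and Cox–Snell R² = 0.15 this is 10 / (0.1 × 0.1823) = 548.5, rounded up to 549, and 549 / 0.90 = 610. S and R² are assumptions, since the protocol states neither. This is the criterion for a binary outcome, and the two sample-size papers in the reference list are titled for continuous and for binary or time-to-event outcomes. It fixes n = 549 and 10 candidates for the check below but says nothing about a count model.

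**Step 2. Dispersion.** Let q be the share with zero headache days, and let m and v be the mean and variance of days among the others. Then variance/mean over all patients is

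φ = v/m + q × m.

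Inputs from the protocol, used only as proxies for q:
- Section 1.3.1 gives an incidence of 15–78% at 3 months, so q is about 0.22 to 0.85.
- Section 1 gives up to 54% at 1 year, so q is at least about 0.46.

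Inputs assumed, because the protocol gives no distribution of headache days:
- m = 5, 10 or 14.5 days.
- Non-zero days are 1 plus a beta-binomial on 27 days, with shape parameters summing to 4, 3 and 2 respectively. This gives v/m of 4.22, 4.50 and 4.51.

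Example: q = 0.46 and m = 10 gives φ = 4.50 + 0.46 × 10 = 9.1.

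**Step 3. False retention.** With unscaled Poisson errors, a covariate with no effect passes a two-sided 5% test with probability

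2 × (1 − Φ(1.96 / √φ)).

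| φ | 1 | 2 | 4 | 6 | 8 | 12 | 15 |
|---|---|---|---|---|---|---|---|
| Retention | 5% | 17% | 33% | 42% | 49% | 57% | 61% |

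A rate of one half needs φ = (1.96 / 0.6745)² = 8.44.

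**Step 4. Simulation of the selection itself.** Set-up: n = 549, 10 independent noise covariates, Poisson backward elimination at p<0.05 (assumed), 120 data sets per setting. Each cell gives φ and the share of noise covariates kept.

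| Zero share q | m = 5 | m = 10 | m = 14.5 |
|---|---|---|---|
| 0 | 4.2; 33% | 4.5; 36% | 4.5; 37% |
| 0.22 | 5.3; 41% | 6.7; 45% | 7.7; 48% |
| 0.46 | 6.6; 44% | 9.1; 49% | 11.2; 55% |
| 0.85 | 8.4; 52% | 12.9; 58% | 16.8; 63% |

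That is 3.3 to 6.3 of 10 noise covariates, against 10 × 0.05 = 0.5 intended. With dispersion-scaled standard errors the share kept was 4–6% in every setting. At a laxer retention level of 0.157, the Poisson share was 47–52% with no zeros and 54–74% with 22–85% zeros.

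**The case against.** The strongest reply has four parts.

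- **The wording is not binding.** The Poisson sentence is introduced as an example, and backwards selection is to be used only where appropriate. Variance handling and the retention level could be settled in an analysis plan that is not shown. This stands in part: a reader might infer that unscaled Poisson is irrevocably fixed, and the text does not say so. But Poisson is the only count model named, and headache days is the only count it can apply to.
- **Safeguards are stated.** An assumption check could expose overdispersion, and bootstrapping and shrinkage temper overconfident predictions. This also stands in part. However, the check applies to models already produced. No action on failure is given, and nothing says selection would be rerun. Shrinkage scales coefficients and does not take out biomarkers already selected. The Delphi reduction in section 14.3 shortens the candidate list without correcting the tests.
- **The dispersion is assumed.** The incidence figures concern post-traumatic headache, whereas the diary records any headache, so the true zero share may be lower. Taking the zero share alone (v = 0) with m = 8, an affected share of 22%, 54%, 65% or 78% gives φ = 6.2, 3.7, 2.8 or 1.8, and retention of 43%, 31%, 24% or 14%. True predictors such as baseline headache would also absorb some dispersion: halving φ = 9.1 to 4.55 lowers retention from 52% to 36% by the Step 3 formula. This is why only a range can be given. A reader might infer that about half of noise biomarkers will be kept. That is a mid-range value under these assumptions, not a property of the plan.
- **Two further inferences fail.** A reader might conclude that missed diary days will bias the count downwards. Section 14.4 names multiple imputation and describes the outcome as a mean, so the text does not establish this. A reader might also expect predictions above 28 days. Poisson permits them, but no such frequency was calculated, and a negative binomial model permits them too.

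**Conclusion.** The point holds as a weakness in the one count model that section 14.4 names. For a count bounded at 0–28, with probable excess zeros and wide spread, unscaled Poisson tests would keep roughly a third to 60% of noise predictors instead of 5%. This assumes dispersion of about 4 to 17 and retention at p<0.05. The direction is robust: even the lowest case considered, 14%, is almost three times nominal, and it allows no variation at all among those with headache. The exact size is not established, because the protocol gives neither quantity. The stated safeguards could lead the analysts to notice the problem, but as written they do not ensure that selection is corrected. The consequence is limited to the headache model, a secondary outcome. The plan should be changed, but the point does not threaten the main result.

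**What to change.** In section 14.4, replace Poisson for headache days with a beta-binomial model of headache days out of completed diary days. State that backwards selection, bootstrap validation and shrinkage are all run under that model, and give the retention level. The model respects the diary limit, estimates the extra variation and uses the number of days actually completed.

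As a fallback, name dispersion-scaled or negative binomial regression with log completed days as an offset, noting that its predictions are not bounded by the diary length. Add one line saying that if the check of assumptions fails, selection is repeated under the replacement model. The return to 4–6% shown above was simulated for dispersion-scaled errors. The beta-binomial was not simulated, so its fit to the zeros should be part of that check.

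The cost is a sentence or two of text, standard software, one extra dispersion parameter and wider intervals. Fewer biomarkers will probably be retained.
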